# 14.2 Trial analysis sets

All screened subjects will be accounted for in the clinical trial report (CTR).

In this open-label safety trial with an as-needed treatment regimen, all eligible subjects could potentially receive treatment with twice-daily delgocitinib cream 20 mg/g. Therefore, only the safety analysis set is defined and used as the basis for the analysis of all endpoints.

The safety analysis set is defined as all enrolled subjects.

The decisions regarding inclusion/exclusion of subjects or subject data from the safety analysis set will be documented in the analysis set definition document.

#### 14.3 Statistical analysis

## 14.3.1 Disposition of subjects

The reasons for permanent discontinuation of IMP and withdrawal from trial will be presented for all subjects in the safety analysis set.

Page 82 of 121

## 14.3.2 Demographics and other baseline characteristics

Descriptive statistics of demographics and other baseline characteristics will be presented for all subjects in the safety analysis set.

Demographics include age, sex, ethnicity, and race. Other baseline characteristics include height, weight, body mass index, Fitzpatrick skin type, duration and classification of CHE, age at diagnosis of CHE, concurrent diagnoses (from medical history and indications for concomitant medication), concomitant medication, number of flares in the past 12 months, previous chronic hand eczema treatments, and IGA-CHE and HECSI scores at baseline in the parent trial.

# 14.3.3 Exposure and treatment compliance

Based on the attended visits data, exposure to treatment will be presented for the safety analysis set as days of exposure during the trial.

The total amount of IMP used during the trial will be summarised for the safety analysis set.

Treatment compliance will be presented for the safety analysis set as the percentages of missed applications during on-treatment periods, derived from the eDiary.

# 14.3.4 Analysis of primary endpoint

The analysis of the primary endpoint, number of treatment-emergent AEs from baseline up to Week 38 is described in Section 14.3.8.1.

# 14.3.5 Analysis of secondary endpoints

The analysis of the secondary endpoints will be based on the safety analysis set.

IGA-CHE and HECSI scores will be summarised at each scheduled visit from baseline up to Week 36 based on observed data.

In addition, the proportion of the subjects achieving IGA-CHE score of 0 (clear) or 1 (almost clear), HECSI-75 and HECSI-90 will be summarised at each scheduled visit from baseline up to Week 36, where subjects who discontinue treatment with IMP prior to Week 36, initiate rescue treatment, or withdraw from the trial, whichever comes first, will be imputed as non-responders.

In the derivation of HECSI-75 and HECSI-90 the baseline score from the parent trials will be used.

THIS DOCUMENT CONTAINS CONFIDENTIAL INFORMATION AND MUST NOT BE COPIED OR MADE AVAILABLE TO ANY THIRD PARTY WITHOUT THE PRIOR WRITTEN CONSENT OF THE LEO PHARMA GROUP

Trial ID: LP0133-1403 Date: 03-Apr-2023

Page 83 of 121

Version: 4.0, Final

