If no improvement is observed after a continuous on-treatment period of 16 weeks with twice-daily delgocitinib cream 20 mg/g, it will be at the discretion of the investigator to evaluate if the subject will benefit from further treatment with delgocitinib cream 20 mg/g.

If CHE becomes 'intolerable', the subject should contact the investigator for an unscheduled visit. Rescue treatment for CHE may be provided to subjects at the discretion of the investigator. In this case, delgocitinib cream 20 mg/g will be discontinued immediately and the subject will be withdrawn from the trial (see Section 9.5).

At Week 36, subjects will attend an end-of-treatment visit. If treatment for CHE is required beyond the end-of-treatment visit, subjects will be referred to standard of care treatment at the discretion of the investigator.

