#### 9.5 Rescue treatment

If medically necessary (i.e. to control intolerable CHE signs and symptoms), rescue treatment for CHE may be prescribed to trial subjects at the discretion of the investigator. The investigators should make every attempt to conduct safety and efficacy assessments (e.g. safety laboratory assessments, disease severity scores) immediately before administering any rescue treatment. If rescue treatment is initiated, the subject must discontinue treatment with delgocitinib cream 20 mg/g immediately and will not be allowed to restart treatment. Subjects who discontinue delgocitinib cream 20 mg/g will be asked to attend an early termination visit at the site. A follow-up visit (performed via phone, but can be a site visit if needed) will be performed approximately 2 weeks after the early termination visit. The subjects will then be withdrawn from the trial (see Section 10.3 for details).

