#### 10.2 Reasons for discontinuation of IMP

Subjects will permanently discontinue IMP in the event of:

- An AE that, in the judgement of the investigator or sponsor's medical expert, contraindicates further dosing.
- Evidence of pregnancy.
- Initiation of rescue treatment.
- Lack of efficacy.
- Clinically important laboratory abnormalities:
  - Alanine aminotransferase (ALT) and/or aspartate aminotransferase (AST) values >3× upper limit of normal (ULN) with total bilirubin >2×ULN (unless elevated bilirubin is related to Gilbert Meulengracht Syndrome) and at the discretion of the investigator.
  - o Confirmed ALT and/or AST values >5×ULN (for more than 2 weeks).
- Positive reaction to IMP patch test.

It is not allowed to restart IMP treatment after permanent discontinuation of IMP.

Page 51 of 121

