# 14.3.12 General principles

If nothing else is stated, an observed-cases approach will be used for tabulations of data by visit (that is, involving only those subjects who attended each specific visit).

Baseline measurements will be defined as the latest available observation at or prior to the baseline visit (Day 1), unless otherwise specified (e.g. baseline of the parent trial will be used for responder's definition of HECSI-75/90).

Categorical data will be summarised using the number and percentage of subjects in each category. Continuous data will be summarised using the mean, median, quartiles, SD, minimum, and maximum values.

Data will be presented for the total cohort of subjects, as well as the combination between randomised treatment in the parent trial (delgocitinib 20 mg/g or cream vehicle) and IGA-CHE TS status at baseline (IGA-CHE 0/1 or  $\ge 2$ ), when appropriate.

Any changes from the statistical analyses planned in this clinical trial protocol will be described and justified in a protocol amendment, the statistical analysis plan, and/or in the CTR, depending on the type of change.

Page 87 of 121

All statistical analysis will be based on the safety analysis set.

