# 14.3.13 Handling of missing values

For binary response tabulations, subjects experiencing discontinuation of IMP, initiation of rescue treatment, or withdrawal from trial, will be imputed as non-responders. Otherwise, missing values will not be imputed.

Page 88 of 121

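### By-visit IGA-CHE and HECSI score summaries use attendees only, and no planned table is stated to include the scores collected when treatment failures leave, so later visits may look better through attrition

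*Combined protocol and SAP*

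**What the plan says.** **Score summaries.** Two of the five secondary endpoints are the IGA-CHE score and the HECSI score by visit. For these, Section 14.3.5 says that "IGA-CHE and HECSI scores will be summarised at each scheduled visit from baseline up to Week 36 based on observed data". Section 14.3.12 explains the observed-cases approach as "involving only those subjects who attended each specific visit", and adds that "Continuous data will be summarised using the mean, median, quartiles, SD, minimum, and maximum values". Section 14.3.13 imputes nothing outside the binary responses.

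**Responder endpoints.** For the other three secondary endpoints (IGA-CHE 0/1, HECSI-75 and HECSI-90), "subjects experiencing discontinuation of IMP, initiation of rescue treatment, or withdrawal from trial, will be imputed as non-responders".

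**Exits.** Section 10.2 opens its list with "Subjects will permanently discontinue IMP in the event of"; rescue treatment and lack of efficacy are both on it. Section 9.5 states: "If rescue treatment is initiated, the subject must discontinue treatment with delgocitinib cream 20 mg/g immediately and will not be allowed to restart treatment". Section 7.1 says that after rescue "delgocitinib cream 20 mg/g will be discontinued immediately and the subject will be withdrawn from the trial". Under Section 10.3, a subject who permanently discontinues is asked to attend only an early termination visit and a safety follow-up.

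**Exit data.** The Section 4 schedule assigns the Week 36 procedures, including IGA-CHE and HECSI, to the early termination visit, which has no week number. For the time just before rescue, Section 9.5 adds: "The investigators should make every attempt to conduct safety and efficacy assessments". No section places these values in a scheduled-visit table or in any other efficacy summary.

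**The concern.** Rescue is meant for hand eczema that has become intolerable. A subject who leaves for that reason, or for lack of efficacy, probably has a high score on leaving and contributes no score afterwards. A table of attendees then loses its worst scores as time passes, and the summary can drift downwards although nobody has improved.

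The plan already treats these exits as informative in the responder endpoints, where leavers count as failures. The score summaries from the same two instruments have no such protection and no sensitivity summary.

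What is at stake is how the long-term efficacy objective is read. The trial has no control arm, so no comparison would reveal an improvement produced by attrition. Section 14.3.11 also says that analyses of these data will support a marketing submission. The same observed-case rule covers the HESD and other patient-reported score summaries.

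**Working it through.** **Inputs from the documents.** About 600 subjects are expected, out of 920 in the parent trials (Section 14.1). The ratio, 600/920 = 65.2%, describes roll-over into this trial and not retention within it. The documents give no dropout rate for this trial, no mix of exit reasons, no expected scores and no SDs. The plan therefore has no figure of its own to reproduce on this point.

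**Formula.** Suppose no subject's score changes. Let d be the fraction that has left, s the leavers' mean exit score and m the stayers' mean.

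- Mean with exit scores retained: (1 − d)m + ds
- Observed-case mean: m
- Apparent improvement due to attrition: (1 − d)m + ds − m = d(s − m)

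The difference is positive only if s > m. It is zero if leavers resemble stayers, and it reverses if leavers score better.

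**HECSI, assumed values.** Take m = 20 and s from 40 to 80, with every leaver a treatment failure.

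| d | d × (40 − 20) | d × (60 − 20) | d × (80 − 20) |
|---|---|---|---|
| 5% | 1 | 2 | 3 |
| 10% | 2 | 4 | 6 |
| 20% | 4 | 8 | 12 |
| 30% | 6 | 12 | 18 |

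**Mixed reasons for leaving.** If only a share f of exits is failure-related and the other leavers resemble stayers, the shift is d × f × (s − m). With d = 20%, m = 20 and s = 60 it is 0.20 × f × 40:

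- f = 25%: 2 points
- f = 50%: 4 points
- f = 75%: 6 points
- f = 100%: 8 points

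**IGA-CHE as categories.** IGA-CHE is a 5-point ordinal scale, so a table of counts is at least as likely as a mean. Assume that 240 of 600 subjects are at 0 or 1 throughout and that only the others leave.

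| Attrition | Still observed | At 0/1, observed cases | At 0/1, leavers as non-responders |
|---|---|---|---|
| 5% | 570 | 240/570 = 42.1% | 240/600 = 40% |
| 10% | 540 | 240/540 = 44.4% | 40% |
| 20% | 480 | 240/480 = 50.0% | 40% |
| 30% | 420 | 240/420 = 57.1% | 40% |

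The effect therefore does not depend on IGA-CHE being shown as a mean. The last column shows why the responder endpoints are protected.

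**The case against.** The strongest reply is that this is a descriptive, open-label safety trial with no comparative analysis, and that treatment failure can be seen elsewhere. Three of the five secondary endpoints count leavers as non-responders. Section 14.3.1 presents the reasons for discontinuation and withdrawal. Section 14.3.6 counts rescue and discontinuation as events in the time to first IGA-CHE ≥2, although only for former delgocitinib subjects with treatment success at Week 16. This reply stands as a limit on importance. It does not change what the two score summaries would show.

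A reader might also infer more than the documents support:

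- **That the curves will improve through attrition.** This depends on leavers scoring worse and on how many there are. Neither is known.
- **That missing scores are missing because the disease was bad.** This is plausible for rescue and lack of efficacy. Sections 10.2 and 10.3 also cover exits for adverse events, pregnancy, laboratory abnormalities, a positive patch test and withdrawal for any reason, which need not reflect bad disease.
- **That every failure leaves by rule.** Giving rescue is the investigator's decision, and so is stopping after 16 continuous weeks without improvement. Lack of efficacy is listed without a definition. A poor responder may stay to Week 36 and remain in the tables.
- **That the exit scores are discarded.** The plan is silent and does not say so. Section 14.3.12 also allows changes to the analyses to be described in a statistical analysis plan, where a mapping rule could appear.
- **That the score and responder tables contradict each other.** They are two declared summaries with different rules. They may diverge, but that is not an inconsistency in the plan.

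**Conclusion.** The point holds in conditional form. The two score summaries are observed-case, failure-related exits end scheduled efficacy assessment, and no planned table is stated to use the scores taken on exit. If leavers score worse than stayers, later-visit summaries look better by d × (leaver mean − stayer mean).

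The direction rests on that one assumption, which is reasonable for subjects rescued for intolerable disease. The size cannot be derived. The 1 to 18 HECSI points in the first table rest wholly on assumed inputs and on every exit being a failure, and the shift falls in proportion to the failure-related share of exits. No percentage bias should be attached to this trial.

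The responder endpoints and the primary safety endpoint are not affected. This is an inexpensive improvement to two descriptive secondary endpoints and not a flaw in the trial's main result.

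**What to change.** Keep the observed-case by-visit table and print the number of subjects observed at each visit.

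Add an end-of-treatment summary of IGA-CHE (counts by category) and HECSI, with this order of precedence:

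1. the Week 36 value, where there is one;
2. for subjects who left after rescue, the last value at or before rescue;
3. for subjects who left without rescue, the early termination value.

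The order needs stating because the early termination visit takes place as soon as possible and may follow the start of rescue. Report how many subjects fall under each source and how many have no usable value. Pre-rescue scoring is best effort, and assessments at unscheduled visits are largely at the investigator's discretion, so some values will be missing.

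A repeated-measures or multiple-imputation summary of HECSI is optional. It brings an assumption about the missing data and must cope with scores that depend on on/off treatment cycles, which is a trade-off in a descriptive single-arm trial.

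**Cost.** One or two extra tables and a few sentences in the analysis section or the statistical analysis plan, with no new assessments. The drawback is that the exit score stands in for a Week 36 score that was never observed, and the table footnote should say so.

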## 14.3.6 Analysis of other/exploratory endpoints

All analyses are based on safety analysis set.

The number of on-treatment days from baseline up to Week 36 will be summarised.

The number of on-treatment periods from baseline up to Week 36 and the rates per 100 person years of observation time will be presented.

The proportion of response days (days with IGA-CHE 0 or 1) from baseline up to Week 36 will be summarised. Mean duration of on-treatment periods per subject from baseline up to Week 36 will be summarised.

Time to first IGA-CHE score ≥2, initiation of rescue treatment, or discontinuation of IMP, whichever occurs first, will be presented for the subjects in the safety analysis set who were previously treated with delgocitinib cream 20 mg/g twice daily in the parent trial and achieved IGA-CHE TS at Week 16 in the parent trial. Kaplan-Meier curve and estimates will be presented. Subjects will be censored at the date of the last assessment visit in case of no events. Follow-up time to first IGA-CHE score ≥2 starts from the baseline visit.

Time to first response (IGA-CHE 0 or 1) will be presented for the subjects in the safety analysis set who did not achieve IGA-CHE TS at Week 16 in the parent trial, by treatment group assigned in the parent trial (delgocitinib cream 20 mg/g or cream vehicle respectively). Kaplan-Meier curves and estimates will be presented. Subjects will be censored at the date of the last assessment visit, initiation of rescue treatment, or discontinuation of IMP, whichever occurs first. Follow-up time to first response will be derived from the baseline visit.

Time to response (IGA-CHE 0 or 1) following treatment re-initiation after first off-treatment period will be presented for subjects in the safety analysis set who were treated with delgocitinib cream 20 mg/g twice daily in the parent trial. Kaplan-Meier curves and estimates will be presented. Subjects will be censored at the date of the last assessment visit, initiation of rescue treatment, or discontinuation of IMP, whichever occurs first. Follow-up time to response will be derived from the visit of treatment re-initiation after first off-treatment period.

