If no improvement is observed after a continuous on-treatment period of 16 weeks with twice-daily delgocitinib cream 20 mg/g, it will be at the discretion of the investigator to evaluate if the subject will benefit from further treatment with delgocitinib cream 20 mg/g.

The investigator will use clinical judgement to treat any symptoms connected with an overdose.

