#### Data to be recorded in the eCRF

The primary reason for permanent discontinuation of IMP must be recorded in the medical records and on the end-of-treatment form in the eCRF where the following options are available:

- Adverse event
- Death
- Lost to follow-up
- Pregnancy
- Withdrawal by subject
- Lack of efficacy
- Other

If 'adverse event' or 'other' is selected, a specification must be provided in the eCRF. If 'adverse event' is selected, the AE in question will be linked to the discontinuation of IMP. If 'withdrawal by subject' is selected, it will be recorded whether the subject withdrew informed consent or not.

It will also be recorded whether the discontinuation of IMP was related to the COVID-19 pandemic.

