# 10.3 Early termination assessments

#### Permanent discontinuation of IMP

Subjects who permanently discontinue IMP prior to Week 36 will be asked to attend the following visits:

- Early termination visit (as soon as possible).
- Safety follow-up visit (phone visit approximately 2 weeks after attending the early termination visit).

See the schedule of trial procedures (Section 4) for assessments to be done at these visits. The investigator will review any AEs which will be followed up according to Section 13.7, if the subject agrees.

Page 52 of 121

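### Both exploratory time-to-response Kaplan-Meier analyses censor at rescue and IMP discontinuation; label that target and add a cumulative incidence curve for the share who respond (minor, cheap improvement)

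*Combined protocol and SAP*

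**What the plan says.** Section 14.3.6 plans Kaplan-Meier curves and estimates for two time-to-response analyses. One is time to first IGA-CHE 0 or 1 in subjects without IGA-CHE TS at parent Week 16, shown by parent treatment group. The other is time to response after re-initiation following the first off-treatment period, in subjects treated with delgocitinib in the parent trial. The same sentence governs both: "Subjects will be censored at the date of the last assessment visit, initiation of rescue treatment, or discontinuation of IMP, whichever occurs first". Neither Panel 3 nor Section 14 says what the curves are meant to estimate.

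The protocol fixes what follows these two events:

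- **Rescue (Section 9.5):** "the subject must discontinue treatment with delgocitinib cream 20 mg/g immediately and will not be allowed to restart treatment". Section 7.1 adds: "delgocitinib cream 20 mg/g will be discontinued immediately and the subject will be withdrawn from the trial".
- **Permanent discontinuation (Section 10.2):** "It is not allowed to restart IMP treatment after permanent discontinuation of IMP". Section 10.3 then leaves only an early termination visit and a safety follow-up.

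Elsewhere the plan treats the same events as failure. In Section 14.3.6, time to first IGA-CHE ≥2 counts rescue and IMP discontinuation as events. Sections 14.3.5 and 14.3.13 impute subjects as non-responders after IMP discontinuation, rescue or trial withdrawal.

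**The concern.** Kaplan-Meier gives a censored subject the same future chance of response as those still at risk. After rescue or permanent discontinuation, the protocol leaves no such chance on IMP. The planned 1-KM is therefore a hypothetical figure: response had nobody stopped.

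That is a legitimate target, but it requires stopping to be unrelated to prognosis. The plan's own reasons for stopping make this doubtful. Section 9.5 says: "If medically necessary (i.e. to control intolerable CHE signs and symptoms), rescue treatment for CHE may be prescribed". Section 10.2 lists lack of efficacy as a reason for permanent discontinuation. Section 9.2 calls for an investigator review of further benefit in this case: "If no improvement is observed after a continuous on-treatment period of 16 weeks".

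Panel 3 gives the purpose as exploring efficacy of as-needed treatment. A reader may therefore take the height of the curve at Week 36 as the share who respond under that regimen, and for that quantity it is too high whenever stops precede later responses. Time to first response is shown by parent treatment group. If the two groups stop at different rates or times, the excess will differ between the two curves.

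**Working it through.** The plan states no response, rescue or discontinuation rate, and no figure for these endpoints, so there is nothing to reproduce. The direction can be shown in general; the size needs assumptions.

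**Inputs.** Nine 4-week intervals to Week 36 (Panel 2). Assumed: response probability per interval h_r of 0.06, 0.10 or 0.20; net stopping of 5, 10, 20 or 30%. Net stopping is the proportion who would stop by Week 36 if nobody responded. Actual stops before response are fewer, because responders leave the risk set first. The model has no other censoring and covers time to first response only.

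**Formulas.**

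- 1-KM = 1 − (1 − h_r)^9. Equivalently it is Σ K_k·h_r, with K_1 = 1 and K_{k+1} = K_k(1 − h_r).
- Cumulative incidence = Σ S_k·h_r, with S_1 = 1 and S_{k+1} = S_k(1 − h_r − h_d).
- Stopping hazard h_d = 1 − (1 − net)^(1/9) if constant. If all stopping falls in intervals 5-9 (after Week 16), h_d = 1 − (1 − net)^(1/5) in those intervals and 0 before.

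**Direction.** Since h_d ≥ 0, S_k ≤ K_k in every interval. Cumulative incidence therefore never exceeds 1-KM. The two are equal only if no stop precedes a later response.

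**Worked case, 10% response and 10% net stopping.**

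- 1-KM = 1 − 0.9^9 = 61.3%.
- Constant stopping: h_d = 1 − 0.9^(1/9) = 0.0116. Cumulative incidence = (0.10/0.1116) × (1 − 0.8884^9) = 58.7%, an excess of 2.6 points. Actual stops = (0.0116/0.1116) × (1 − 0.8884^9), about 7%.
- Stopping only after Week 16: h_d = 1 − 0.9^(1/5) = 0.0209. Cumulative incidence = (1 − 0.9^4) + 0.9^4 × (0.10/0.1209) × (1 − 0.8791^5) = 60.2%, an excess of 1.1 points. Actual stops are about 5%.

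**All cases at Week 36.** Entries are cumulative incidence in %, with the excess of 1-KM in points in brackets. Differences are taken before rounding.

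| Response per 4 weeks | Net stopping | 1-KM | Constant stopping | Stopping only after Week 16 |
|---|---|---|---|---|
| 6% | 5% | 42.7 | 41.8 (0.9) | 42.3 (0.4) |
| 6% | 10% | 42.7 | 40.9 (1.8) | 41.9 (0.8) |
| 6% | 20% | 42.7 | 38.9 (3.8) | 41.0 (1.7) |
| 6% | 30% | 42.7 | 36.9 (5.8) | 40.0 (2.7) |
| 10% | 5% | 61.3 | 60.0 (1.3) | 60.7 (0.5) |
| 10% | 10% | 61.3 | 58.7 (2.6) | 60.2 (1.1) |
| 10% | 20% | 61.3 | 56.0 (5.2) | 59.0 (2.2) |
| 10% | 30% | 61.3 | 53.3 (8.0) | 57.8 (3.4) |
| 20% | 5% | 86.6 | 85.0 (1.6) | 86.0 (0.5) |
| 20% | 10% | 86.6 | 83.4 (3.2) | 85.5 (1.1) |
| 20% | 20% | 86.6 | 80.1 (6.5) | 84.3 (2.2) |
| 20% | 30% | 86.6 | 76.6 (10.0) | 83.1 (3.4) |

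The late-stopping column reflects the review after 16 continuous weeks in Sections 7.1 and 9.2, but stops can occur earlier. The re-initiation analysis is not quantified, because its follow-up starts at a variable later visit.

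**The case against.** Censoring at IMP stop is a recognised on-treatment choice, and Section 14.3.6 does give population, event, time origin, estimator and censoring rule. This stands: a reader might infer that the Kaplan-Meier analysis is wrong, and the documents do not support that. What is missing is a label and a curve for the other quantity.

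Panel 3 words these endpoints as times, not as a proportion of responders. The share in response is a separate secondary endpoint that already uses a conservative rule. This also stands, so one cannot infer that the plan will overstate its response rates. But the responder tables are visit-specific and do not give the cumulative share who have responded by a given time.

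Section 14.3.1 reports reasons for discontinuation and withdrawal, and Section 14.3.12 allows display by parent treatment and baseline status when appropriate. A careful reader could then see how many subjects stopped and why. That helps interpretation but does not correct the curve.

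The size is wholly assumed. The 10.0-point case combines the highest response, the highest net stopping and constant stopping. Section 8.3 excludes subjects who stopped IMP or used rescue in the parent trial, which may remove some early stoppers. Ten points should not be read as expected.

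No test, error rate or decision is affected: Section 14.1 rules out comparative analyses. Finally, Section 14.3.12 mentions a statistical analysis plan as a place for changes. No separate text of one was available, so a target stated there could not be checked.

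**Conclusion.** The point holds as a minor, cheap improvement. For both analyses the planned 1-KM is a figure for a setting in which nobody stops IMP, under an independence assumption that the protocol's own stopping reasons make doubtful. It is at or above the share who actually respond on as-needed treatment; that direction needs no assumed rates. The size does: for time to first response it is 0.4 to 10.0 points at Week 36 over the ranges shown, and 1.1 to 2.6 points at 10% response per 4 weeks and 10% net stopping.

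A reader might go further and infer a biased comparison between the parent treatment groups. The documents give no stopping rates by group and plan no comparison, so only the possibility of unequal excess can be stated.

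**What to change.** 1. Keep both Kaplan-Meier analyses and label them as response while on IMP without rescue, stating the independence assumption.
2. For both analyses, add an Aalen-Johansen cumulative incidence of response. Treat rescue, permanent IMP discontinuation and trial withdrawal as competing events, matching the failure rule in Sections 14.3.5 and 14.3.13. Otherwise censor at the last assessment visit.
3. As a sensitivity analysis, censor loss to follow-up and COVID-19-related stops instead of counting them as competing events.
4. Use the cumulative incidence for any statement of the share of subjects who respond.

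The data are already collected. Section 9.6 records the rescue flag and start date. Section 10.2 covers the reason: "The primary reason for permanent discontinuation of IMP must be recorded in the medical records". The COVID-19 relation is recorded under Sections 10.2 and 11.9, and the date of last application under Section 11.9. The cost is a few lines of SAP text, a standard procedure, one more display per analysis and a slightly lower response figure.
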